Title: RCT of Mindfulness-Enhanced Pivotal Response Group Treatment on Parenting Stress

NCT# not yet assigned

Document date: 6/1/2023

Study Protocol and Statistical Analysis Plan

Participants

A total of 15 caregivers and children will be randomly assigned to mPRT or pPRT groups. Inclusion criteria for children includes the following: 1) current or suspected ASD diagnosis, verified by ADOS-2, brief clinical interview, and expert clinical opinion using DSM-5 criteria; 2) demonstrates ability to make meaningful vocalizations; 3) no active medical problems (e.g., unstable seizure disorder). Inclusion criteria for participating caregiver includes the following: 1) no severe mental health problems (e.g., suicidal intent; psychosis); 2) willingness to record weekly videos and share in a group setting.

Participants will be recruited from Southwest Virginia via multiple methods (e.g., university and non-university clinics, registries, local ASD support groups, parent resource centers, local service agencies or schools). A two-stage eligibility process will be used. First, caregivers who expressed interest in the study will complete a phone interview to screen for study eligibility. Caregiver and child dyads who appeared to meet eligibility criteria and who were still interested in the study based on the phone screen will then be scheduled for a two-session assessment appointment to confirm diagnosis and eligibility.

Procedure

All interested families will complete a phone screen to determine initial eligibility criteria. Those who qualify will be invited to participate in two screening visits at the VT Autism Clinic (approximately 3.5 hours total). Parents will be provided with the option to complete all components in one day or two days. During these visits, a clinician will administer the Autism Diagnostic Observation Schedule- 2nd Edition (ADOS-2) to the child and the participating

caregiver to confirm the child's diagnosis of ASD, as well as the Mullen Scales of Early Learning (MSEL), a measure of cognitive ability.

Parents will engage in a 15-minute task with their child to measure baseline levels of child utterances and baseline fidelity of PRT techniques. This task is called the Structured Laboratory Observation (SLO) and will be modeled from Hardan et al. (2014). During the first five minutes, parents will be instructed to sit quietly and watch their child play (i.e., do not initiate interactions; however, parents can respond if child initiates). This period allows the child to become acquainted with the room and materials. Then, parents will be instructed to elicit language from the child for 10 minutes, using whatever strategies they want. Immediately following the SLO, parents will be asked to provide self-reported perceptions of positive and negative mood and stress levels during the parent and child interaction. In addition to measuring baseline child utterances with a caregiver, all children will engage in a 10-minute SLO with a trained PRT clinician to control for baseline levels of fidelity of PRT techniques. Finally, parents will complete paperwork to determine demographic information, child language and social behaviors, as well as levels of parenting stress, parent feelings toward child, and mindfulness.

Data will be collected over the course of four time points (pre-treatment, mid-treatment, post-treatment, 3-month follow-up) and weekly. See Table 1 for the complete battery at each timepoint. All questionnaire data will be collected either via paper and pencil or sent from and stored electronically through an online system called Research Electronic Data Capture (REDCap; Harris, Taylor, Thielke, Payne, Gonzalez, & Conde, 2009), hosted at Virginia Tech. REDCap is a secure, web-based application designed to support data collection for research studies. Weekly measures include a 10-minute home video of a participating parent interacting with his or her child while implementing PRT strategies and eliciting language. These videos will

be used in treatment to review strengths, areas of growth, and barriers encountered in the naturalistic settings as well as in research to monitor changes in child utterances and percentage of fidelity of implementing PRT strategies. In an effort to decrease demands from parents, we will provide families with Android tablets and instructions on how to upload the videos.

Randomization. Eligible families will be randomly assigned to either the mindfulness enhanced mPRT or to pPRT as the control condition. The Randomization Module in REDCap will be completed by a research assistant, blind to the clinician completing the pre-treatment assessment. Groups will be matched on gender of caregiver to control for gender differences previously reported in parenting stress literature (Davis and Carter, 2008). Both caregivers are permitted to attend groups; however, one caregiver must identify as the primary reporter (i.e., individual who completes all self- and parent-report questionnaires, attends sessions regularly, and participates in all home videos).

If challenges with recruitment emerge, randomization rules may be adjusted. In this instance, once the period of recruitment has commenced and 3 or more families have completed the pre-assessment condition, a random number generator will be used to determine the group for the individuals.

Treatment (Appendix A). All families will receive the same dose of PRT parent training delivered in a previously studied package (e.g., Hardan et al., 2014) that includes 16 hours of group sessions and 4 hours of individual sessions, delivered over a 12-week timeframe. The format for teaching PRT techniques and abilities will be replicated from Hardan et al. (2014), who adapted the material from the manual, “How to Teach Pivotal Behaviors to Children with Autism” (Koegel et al., 1989) and has been previously implemented in a feasibility study by the current researchers.

Additionally, all parents will receive 6 hours total of group supplemental treatment that specifically targeted parenting stress either by mindfulness-based techniques or by psychoeducation (depending on random assignment). Materials from the psychoeducation group include didactic training on a variety of topics focusing on the parent, child and family outcomes. For example, literature on general parenting stress as well as parenting stress in parents of children with ASD was one topic presented in an informational manner, without providing instruction regarding specific skills training.

The mindfulness-enhanced treatment, on the other hand, provides specific skills as well as didactic information about applying mindfulness to the parenting role. Components from ACT as well as Mindful Parenting will be incorporated into the weekly sessions in a manner that applied the mindfulness skills to the newly learned PRT skills.

Measures

Eligibility and sample characterization.

Autism Diagnostic Observation Schedule, Second Edition (ADOS-2; Lord et al., 2012).

The ADOS-2 is a semi-structured, observational assessment of ASD characteristics and is one of the gold standard tools used to assess social communicative and repetitive behaviors in children who are suspected of having ASD. The ADOS-2 consists of multiple modules, which are determined by age and language ability. The Toddler Module and Module 1 are administered to children with no or little verbal language and Module 2 is used for children with phrase, but not verbally fluent, speech. The ADOS-2 demonstrates moderate to high levels of internal consistency, moderate test-retest reliability, and acceptable interrater reliability (McCrimmon & Rostad, 2014).

Mullen Scales of Early Learning (MSEL; Mullen, 1995). The MSEL measures developmental functioning for young children, specifically in visual, linguistic, and motor domains. Additionally, the MSEL distinguishes between receptive and expressive language abilities. The MSEL demonstrates good internal consistency and high test-retest reliability (Mullen, 1995).

Treatment feasibility and acceptability.

Parental adherence to treatment. Treatment adherence will be measured by the number of weekly videos provided, as these were crucial components of treatment in regard to teaching and providing feedback. Parents will also receive weekly questionnaires inquiring how often they practiced PRT techniques during the past week and ranged from 0 (Not at all) to 4 (Every day). Averages will be calculated accounting for the amount of questionnaires they completed.

Treatment satisfaction. The participants' satisfaction with the treatment components will be assessed at the post-treatment time point. First, participating caregivers rate their satisfaction with the overall program. Then, parents rate their perceived difficulty and helpfulness of the treatment components (i.e., PRT specific concepts as well as the individual's assigned supplemental group). The satisfaction survey also includes open-ended responses to better understand the components that parents viewed as most helpful, least helpful, and recommendations for future groups.

Treatment efficacy: Primary outcome variables.

Therapist fidelity of treatment implementation (Appendix B). A licensed clinical psychologist trained in PRT will view 5-6 group sessions out of the 11 total group sessions (i.e., 45 to 54% of the total group sessions) to assess for therapist fidelity of treatment implementation. The videos will be randomly assigned for viewing before all groups commenced and the

randomization was blind to treatment providers. Fidelity will be assessed on completion of specific session goals, therapeutic relationship, and level of group engagement.

Child utterances (Appendix C). The level or amount of child utterances during in-laboratory semi-structured tasks and in-home naturalistic environments will be coded by trained undergraduate research assistants using *Noldus The Observer XT* (version 12.0 software, Noldus Information Technology, Leesburg, VA, USA). All videos will be double coded by undergraduate research assistants who were blinded to treatment condition and treatment phase. Three total coders will complete double coding for all videos. Interrater reliability will be assessed by Kappa and Rho, due to the complexity of the coding system. All research assistants will attend group training in behavioral coding and child utterances and will attain above 80% fidelity with sample videos coded by a master's level clinician. As modeled in Hardan et al. (2014), child utterances consist of the following: unintelligible (e.g., sound produced by child that does not appear to demonstrate an attempt at a meaningful utterance; "lalalala"), imitative (e.g., parent models the word and encourages child to imitate exact word), verbally prompted (e.g., parent asks a question with open-ended response), nonverbally prompted (e.g., parent presents an opportunity for language by holding an object in sight and out of reach) and spontaneous (i.e., not prompted by the parent). To reduce variability, the amount of child utterances was expected to increase in both groups from pre SLO to post and follow-up SLO. Amount of child utterances were examined to determine effectiveness of treatment across groups.

In the current study, differences in child utterances will be calculated using changes in SLO and weekly videos will also be used to estimate changes in average utterances from weeks 1 and 2 to weeks 9 and 10. Because frequency/total counts were used for analyses, weekly videos will be excluded from analyses if they were less than 9 minutes in length.

Parent fidelity of PRT implementation (Appendix D). Parent fidelity of PRT

implementation will be coded by trained undergraduate research assistants using *Noldus The Observer XT* to measure changes in level of fidelity in-laboratory semi-structured tasks and in-home naturalistic environments over the course of treatment. All videos, including SLOs at all 4 timepoints as well as weekly videos (averaged for weeks 1-2 and weeks 9-10) will be coded by two research assistants separately (i.e., each research assistant coded all the videos separately). After videos were double-coded, the two research assistants will meet together to complete final consensus coding. All research assistants will attend group training in behavioral coding, behavioral management, and PRT techniques; they will attain at least 80% fidelity with two sample videos coded by PhD and master's level clinicians who were certified in PRT. Standardized measures of PRT fidelity (e.g., Bryson, Koegel, Koegel, Openden, Smith, & Neft, 2007; Minjarez et al., 2011) will be adapted for the current project to accommodate measurement every 30 seconds (as opposed to 1- or 2-minute intervals).

Fidelity of PRT implementation will include 5 total over-arching techniques (i.e., shared control, providing clear opportunities, interspersing maintenance trials, reinforcing attempts, and contingent/natural reinforcement of appropriate behavior), which could be further divided into 10 total components (i.e., following child's lead/child choice, natural reinforcer, attending to task, clear instructions, maintenance, task variation, natural, immediate, appropriate and attempts). The *Noldus* system will be automatically programmed to stop a video after every 30 seconds and prompt the research assistant to input fidelity information for all 10 components in a binary form (i.e., parent either achieved correct performance of component for the entire interval or did not, coded as 1 or 0 respectively). Total correct percentages will be calculated for each component and then averaged over the number of intervals to create a final correct percentage for total PRT

fidelity. Because final percentages will be individually calculated based on the total time they were coded, videos that range in length from 5 minutes to 10 minutes will be used for the current set of analyses.

Parenting Stress Index, Fourth Edition (PSI-4; Abidin, 2012). The PSI-4 is the most widely used measure of parenting stress, not only in ASD but all parenting literature. The PSI-4 focuses on three domains of parenting stress: those relating to child characteristics, those attributed to parent characteristics as well as situational and life stressors. The PSI demonstrates strong internal consistency (alpha .96 or greater for each domain and test-retest reliability ranging from .65 to .96 for the Total Stress score). The PSI-4 child domain will be measured at four time points to measure change in parenting stress relating to child characteristics as a result of treatment.

Autism Parenting Stress Index (APSI; Silva & Schalock, 2012). The APSI consists of questions specific to parenting stress for parents of young children with ASD, such as behavioral symptoms and core deficits. Parents rate how much stress specific aspects of their child's health yield, ranging from "Not stressful" to "So stressful sometimes we feel we can't cope." The original validation of the measure was completed with a sample of children with ASD, other developmental disorders, and typical development. The APSI demonstrated good internal consistency ($\alpha = .83$) within the ASD population as well as high test-retest reliability ($r = .88$) for parents of children with ASD over a 4-month period of time.

Subjective Units of Parenting Stress Scale (Appendix E). An adaptation of the Subjective Units of Distress Scale, previously utilized in Singh et al., 2007, will be used to assess for levels of parenting stress immediately following all 10-minute SLOs.

Exploratory outcome variables.

Positive parent feelings toward child.

Parent Feelings Questionnaire (PFQ; Deater-Deckard, 2000). The PFQ (Appendix F) consists of 24 items rated on a 5-point Likert-type scale and measured self-report of personal negative and positive feelings toward the child participating in treatment. The items include statements about feelings toward the child participating in the study. For example, “Sometimes my child can really test my patience” and “I find it easy to praise and compliment my child, especially for good behavior” are questions from the negativity sub-scale and positivity subscale respectively. Previous literature demonstrates good internal consistency for both the positivity scale (Cronbach’s alpha = .88) and negativity scale (Cronbach’s alpha = .90; Wang, Deater-Deckard, & Bell, 2013). The positivity scale will be used to assess group differences over time.

Positive and Negative Affect Schedule (PANAS; Crawford & Henry, 2004). The PANAS (see Appendix G) is a reliable and valid measure of positive and negative affect in adults. Previous literature demonstrates good internal consistency for the Positive Affect scale ($\alpha = .89$) and .Negative Affect scale ($\alpha = .85$). For the current study, the instructions for the PANAS were adapted to assess level of parent affect during parent-child interactions in clinic (i.e., during each SLO). The positive affect scale will be used to measure changes over time.

Parent mindfulness.

Five Facet Mindfulness Questionnaire (FFMQ; Baer et al., 2006). The FFMQ (Appendix H) is a 39-item self-report measure that assesses one’s general propensity towards mindfulness in daily life. The FFMQ consists of 5 subscale scores (i.e., non-reactivity to inner experience, observing, describing, acting with awareness, and non-judging of inner experience) that load onto a total mindfulness score. Parents endorse statements on a 5-point Likert scale ranging from

1 (Never or Rarely True) to 5 (Very Often or Always True), with higher scores reflecting increased levels of mindfulness.

Acceptance and Action Questionnaire-II (AAQ-II; Bond et al., 2011). The AAQ-II (Appendix I) is a seven-item measure designed to capture a person's level of experiential avoidance, where each item is ranked on 7 point scale ranging from "never true" to "always true". Higher scores on the measure reflect increased levels of experiential avoidance, the antithesis of psychological flexibility. The AAQ-II demonstrates good internal consistency (i.e., ranging from .78 to .87 across three samples) and acceptable test-retest reliability (i.e., .78 - .88). The AAQ-II will be administered at all time points.

Child problem behavior. The Child Behavior Checklist for Ages 1.5-5 (CBCL/1.5-5; Achenbach & Rescorla, 2001) is a parent report measure on child emotional and behavioral characteristics. Previous research suggests a bidirectional relationship between parent stress and child problem behaviors. Although the treatments in the current study focus on increasing child utterances and reducing parenting stress, changes in child problem behavior are also included to better understand baseline differences and change because of treatment. The CBCL demonstrates good internal consistency in general populations (.89 for internalizing and .92 for externalizing; Achenbach & Rescorla, 2001) as well as ASD specific populations (.80 for internalizing, .90 for externalizing; Pandolfi, Magyar, & Dill, 2009).

Statistical Analysis Plan

All data will be checked for normality, skewness, and kurtosis. In the case of small sample size and non-normal distributions, non-parametric analyses will be used to compare groups and changes over time.

Treatment feasibility and acceptability.

Parental adherence to treatment. Retention rate will be calculated by dividing the number of participants who were considered treatment completers by the total number of participants who were randomly assigned to a group. Because weekly videos were a crucial and core component of the PRT treatment package, the total number of videos submitted by parents will be calculated as a measure of adherence. Finally, parent weekly ratings of the amount of time spent implementing PRT skills in the home environment will be averaged to compare between groups.

Treatment satisfaction. The sections on perceived level of difficulty and helpfulness for PRT strategies will be averaged separately for each group.

Treatment efficacy and exploratory analyses.

Group differences. Pending anticipated non-normal distributions of the small samples, Mann-Whitney U tests will be used to make baseline comparisons to compare independent samples (i.e., completers versus non-completers; mPRT versus pPRT). G*Power3 (Faul, Erdfelder, Lang, & Buchner, 2007) power analyses will be completed to evaluate the size of effect one can be expected to obtain given the obtained sample size, and $\alpha = .05$. A sample size of 95 will be necessary to detect a large effect ($r = .5$). Group comparisons will also be made at post-treatment to analyze differences in parent fidelity of PRT techniques and treatment satisfaction. To calculate effect size, the following formula will be ($r = Z/\sqrt{N}$). The

interpretation of r values are as follows: .5 = large effect, .3 = medium effect, .1 = small effect (Coolican, 2009; Fritz, Morris, & Richler, 2012).

In addition, to test within-group changes, non-parametric Wilcoxon Signed Rank Test (equivalent to a dependent t -test) will be used to compare baseline and endpoint/follow-up scores for each group across variables of interest. A sample size of 27 will be necessary to detect a large effect ($r = .5$) and 648 for a small effect ($r = .1$). Due to low power, effect sizes will also be calculated when determining change as a result of treatment.

Single-Subject Analyses. In addition to group change over time, individual level change will be calculated for parenting stress, parent mindfulness, and parent positive feelings toward child using Reliable Change Index (RCI; Jacobson & Truax, 1991). RCIs will be calculated to determine the magnitude of change needed to show meaningful change above and beyond standard error. RCI calculations will be completed by dividing the difference of scores between two timepoints (i.e., either pre-treatment and post-treatment or pre-treatment and follow-up), divided by the standard difference, which includes test-retest reliability and standard deviation of the original measure. RCI values above 1.96 are suggested to infer statistically significant and meaningful change. The test-retest reliabilities and standard deviations used to compute the S_{diff} score will be obtained from the literature. If test-retest reliability was not previously reported in literature, then Cronbach's alpha was used (from the literature).

Table 1
Assessment Schedule

Construct/ Measure	Pre-Tx	Mid	Weekly	Post-Tx	Follow-up
Sample Characterization					
ADOS-2	X				
Child History Form	X				
Mullen	X				
Child Behavior Checklist	X				
Treatment Efficacy					
SLO Child Utterances	X	X	X	X	X
Treatment Satisfaction				X	
Therapist Fidelity of Treatment Implementation			X		
Parenting Stress					
PSI-4 (Child)	X	X		X	X
APSI	X	X		X	X
SUPSS	X	X		X	X
Positive Parent/Child Interactions					
PANAS	X	X		X	X
PFQ	X	X		X	X
Parent Mindfulness					
AAQ-II	X	X		X	X
FFMQ	X	X		X	X

Notes. PSI-4 = Parenting Stress Index Fourth Edition; APSI = Autism Parenting Stress Index; SUPSS = Subjective Units of Parenting Stress Scale (completed after 10 minute parent/child interaction); SLO = Structured Laboratory Observation; PANAS = The Positive and Negative Affect Schedule; PFQ = Parent Feelings Questionnaire; ADOS-2 = Autism Diagnostic Observation Schedule Second Edition; SRS-2 = Social Responsiveness Scale Second Edition; AAQ-II = Acceptance and Action Questionnaire; FFMQ = Five Facet Mindfulness Questionnaire

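### The arms are balanced on stress only through caregiver gender, although baseline stress is collected at pre-treatment; with 15 families this leaves a modest chance imbalance that neither the allocation nor the analysis addresses

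*Combined protocol and SAP*

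**What the plan says.** - Participants gives the size: "A total of 15 caregivers and children will be randomly assigned to mPRT or pPRT groups". The allocation ratio is not stated.
- Procedure, Randomization: "Eligible families will be randomly assigned to either the mindfulness enhanced mPRT or to pPRT as the control condition". Caregiver gender is the only balancing factor named. The reason given for it is parenting stress: "Groups will be matched on gender of caregiver to control for gender differences previously reported in parenting stress literature". How the matching is done is not described.
- The same section allows a fallback: "If challenges with recruitment emerge, randomization rules may be adjusted". In that case, once "3 or more families have completed the pre-assessment condition, a random number generator will be used to determine the group". The fallback does not mention gender.
- Procedure describes the paperwork at the screening visits: "Finally, parents will complete paperwork to determine demographic information, child language and social behaviors, as well as levels of parenting stress". Table 1 lists the PSI-4 child domain, the APSI and the SUPSS at Pre-Tx.
- Measures, PSI-4: "The PSI-4 child domain will be measured at four time points to measure change in parenting stress". All three stress scales stand under the primary outcome heading.
- The SAP (Group differences) plans baseline Mann-Whitney comparisons of the arms and within-arm Wilcoxon tests of change. It names post-treatment comparisons between arms only for caregiver fidelity and satisfaction. It states no baseline-adjusted comparison of stress.

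**The concern.** The plan sets out to make the arms comparable on stress, and does so through a proxy when a direct measure is taken from the same caregivers. In a trial of 15 families a proxy that explains little of the variation in stress does little to equalise it. If the arms start apart, two things follow. The arm that starts higher tends to fall somewhat more through regression to the mean, which affects how the two within-arm results look side by side. The gap also adds noise to any unadjusted contrast of mPRT with pPRT on stress, the outcome in the trial's title. Allocation cannot be redone afterwards, and the planned analysis does not adjust for the gap.

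**Working it through.** The plan gives no figure for baseline imbalance, so there is none to reproduce.

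**Inputs.** N = 15 (Participants). Retest reliability of .65 to .96 for PSI Total Stress and .88 for the APSI (Measures). Assumptions: 1:1 allocation (7 v 8), roughly normal scores, a gap of 0.5 SD in either direction as the threshold, and a baseline-to-post correlation r = 0.7 for precision.

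**1. Chance gap with no balancing.** In SD units the difference in arm means has standard error √(1/7 + 1/8) = 0.518.
- P(gap ≥ 0.5 SD) = 2(1 − Φ(0.5/0.518)) = 2(1 − Φ(0.966)) = 33.4%.
- P(gap ≥ 0.8 SD) = 12.2%; P(gap ≥ 1 SD) = 5.3%.
- With other splits, P(gap ≥ 0.5 SD) is 34.3% at 6 v 9 and 36.1% at 5 v 10.

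**2. Effect of matching on gender.** A factor with minority share p and a difference of δ SD explains p(1 − p)δ² of the variance. With 4 of 15 caregivers in the minority gender and δ = 0.5 (both assumed), this is 0.267 × 0.733 × 0.25 = 0.049. The standard error becomes 0.518 × √0.951 = 0.505, and P(gap ≥ 0.5 SD) = 2(1 − Φ(0.99)) = 32.2%. Simulation with 2 to 7 minority-gender caregivers and δ from 0.3 to 0.8 gives 29.7% to 33.1%.

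**3. Would the baseline test detect it?** At 7 v 8, a two-sided Mann-Whitney test at .05 has about 14% power against a true 0.5 SD difference. A non-significant result would not show balance.

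**4. Regression to the mean.** The differential fall from a 0.5 SD gap is (1 − r) × 0.5, with r the retest value:
- r = .65: 0.175 SD
- r = .88 (APSI): 0.06 SD
- r = .96: 0.02 SD

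This is shared between the arms. At r = .88 the standard error of one arm's mean change is √(2 × 0.12)/√7.5 = 0.18 SD.

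**5. Precision of a between-arm stress contrast at r = 0.7, without balancing on stress.**

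| Contrast | SD of the difference |
|---|---|
| Unadjusted post score | 0.518 |
| Change score | 0.518 × √(2 × 0.3) = 0.40 |
| Adjusted for baseline, slope known | 0.518 × √(1 − 0.49) = 0.37 |
| Adjusted, slope estimated | 0.37 × √(1 + 1/(15 − 4)) = 0.39 |

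Ranking families in pairs on stress takes the change-score figure from 0.40 to 0.37–0.39. Adjustment alone therefore recovers nearly all the precision that better allocation could give.

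**6. Balance if stress enters the allocation (simulated).** With pairs ranked on stress within gender, P(gap ≥ 0.5 SD) is:

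| Allocation | P(gap ≥ 0.5 SD) |
|---|---|
| Gender only | about 33% |
| All 15 together | roughly 2–13% |
| Two batches (8 + 7) | about 13–20% |
| Three batches of 5 | about 21–25% |
| Batches of 3 | about 31–33% |

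The first range depends on how unpaired families are handled. One-at-a-time minimisation on high/low stress gives 13–19%. Adding gender as a factor, with an 80% biased coin, gives about 23%.

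**The case against.** The strongest reply is that one in three is a property of 15 families and holds for any baseline variable left unbalanced. The randomisation is valid, and adjustment in the analysis gives most of the benefit without touching the allocation. All of this stands, which is why adjustment comes first in the fix.

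Three further points also stand in part.
- Scoring before allocation is implied, not stated. Eligibility does not depend on the stress paperwork, and questionnaires may be sent electronically. The fallback does place allocation after the pre-assessment.
- Balancing one stress score protects the other scales only through correlations that the documents do not give.
- The number of treatment starts is not stated, and the fallback's minimum of three families is the batch size at which pairing gains almost nothing.

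A reader might infer more than the documents support. Pairing all 15 families takes the SD of an unadjusted post-score difference from 0.52 to 0.40–0.42, a variance ratio of about 1.5 to 1.7 ((0.52/0.42)² to (0.52/0.40)²). That looks like a large saving in families, but the SAP names no such contrast for stress. For change scores the gain is small. A reader might also infer that the within-arm tests would show a spurious benefit. At the APSI's retest value the 0.06 SD effect, shared between arms, is well inside the 0.18 SD standard error of one arm's mean change.

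**Conclusion.** The point holds as a modest weakness of design and analysis. Gender is the only balancing factor, it is there because of stress, and it leaves the chance of a 0.5 SD stress gap at about one in three (30–36% over the splits and gender assumptions tried). No baseline-adjusted between-arm stress comparison is stated.

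It should not be read as biased randomisation: over repeated allocation, chance imbalance favours neither arm. The likely distortion from a 0.5 SD gap is 0.02–0.18 SD, and 0.06 SD for the APSI. Nor is there a fault in matching on gender, which can stay.

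The figures assume 1:1 allocation, roughly normal scores and a 0.5 SD threshold, none of which is in the documents. They apply to one stress score at a time. The .65 to .96 range is quoted for PSI Total Stress and is borrowed here for the child domain. The precision figures assume r = 0.7.

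**What to change.** 1. **SAP, Group differences.** State a between-arm comparison of stress adjusted for the baseline score, for example a rank-based or permutation ANCOVA. This costs wording only and does not depend on how families are recruited.
2. **Procedure, Randomization.** Name one baseline stress score (for example the APSI total), require it to be completed and scored before allocation, and add it to caregiver gender. Where families are allocated in batches, rank them on that score within gender and randomise 1:1 within consecutive pairs, both members at once. State how an unpaired family is handled. Where families are allocated singly, use a high/low stress factor with a cut-point fixed in advance. Apply the same rule to the fallback, and state the expected batch size, since the gain depends on it.

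Cost: one questionnaire scored before allocation, some batching, and a change to the allocation set-up. No extra families, visits or instruments are needed. Balance is improved on one stress score only, and an analysis that ignored that score would be somewhat conservative, so the second change should not be made without the first.
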